Treatment of HCV has been the main focus of clinical research since vaccine research has proved to be difficult, as well as the necessity of treating undiagnosed individuals. Among the 7 major HCV genotypes, genotype 1 is by far the most prevalent in Europe and in the United States. It has historically been the most difficult type to treat. Prior to 2011, the standard treatment for HCV was a combination of once-weekly injectable Pegylated Interferon with daily

oral Ribavirin to be taken for 48 weeks. The cure rate, measured as sustained virologic response (SVR) for this regimen is a dismal 40-50% [6]. Adherence to the treatment was difficult for many patients due to the length of therapy and the associated side effects of both interferon and ribavirin. The addition of new directly acting agents (DAA), Boceprevir and Telaprevir in 2011, revolutionized HCV treatment, increasing cure rates up to 75%. However, adherence continued to plague therapy because of side effects and thrice-daily dosing.

In 2013, 2 new DAA's were FDA-approved, ushering in the interferon-free era of HCV therapy. Sofosbuvir and Simprevir are once daily oral agents with much fewer side effects than any previous anti-HCV medication. Ledipasvir, another oral DAA, has been approved by the FDA in October 2014, to be given as a single tablet regimen together with Sofosbuvir. The length of treatment has also decreased, from 48 weeks to 12-24 weeks, and clinical trials of the combination of these drugs showed cure rates above 90%, with increased tolerability and safety [8]. Other DAA's since then have been approved by the FDA such as the combinations of ombitasvir/paritaprevir/ritonavir (Viekira Pak) and Grazopravir/Elbasvir (**Zepatier**).

are in clinical trials or under FDA review, increasing the chances that more patients can be cured from HCV infection.

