Electronic assisted compliance is not the sole indicator of MEMS, it is also used in conjunction with answers about demographics, clinical state and symptoms to learn more about the patient characteristics that influence whether a medication regimen is adhered to.

Portal724-MEMS is HIPAA Complaint and ISO27001 Certified. The Electronic Data Capture, the Data Transfer and Data Access are all confidential and Secure in every stage of the Data

Flow Model. The device to be used in this study is a Smart Cap with Pill Dispensing and Integrated Cellular Modem.

Objective

Primary: To determine the effect of the use of Portal724-MEMS Service on medication adherence in the treatment of Hepatitis C patients with grazopravir/elbasvir with or without Ribavirin, defined as compliance to regimen 95% of the time.

Methods

Study design: Open-label, randomized, single center pilot study.

Treatment Arms:

Genotype 1a, treatment naïve or PegIFN/RBV experienced without baseline NS5A polymorphisms with elbasvir/grazoprevir for 12 weeks

Genotype 1a, treatment naïve or PegIFN/RBV experienced with baseline NS5A polymorphisms with elbasvir/grazoprevir/ribavirin for 16 weeks

Genotype 1b, treatment naïve or PegIFN/RBV experienced for 12 weeks

Genotype 1a or 1b, PegIFN/RBV/PI-experienced with elbasvir/grazoprevir/ribavirin for 16 weeks

Genotype 4: treatment naïve with elbasvir/grazoprevir for 12 weeks

Genotype 4: PegIFN/RBV- experienced with elbasvir/grazoprevir/ribavirin for 16 weeks

Proposed number of participants: 40 patients infected with HCV (20 for each group)

Data Collection Time Period: approximately 1 year

Site of Enrollment:

Liver Center at Saint Michael's Medical Center. [name].

In the Liver Center, the main Hepatitis / Infectious Diseases Physician that this study will collaborate with is [name], MD.

Study Patient Population

Treatment-naïve and treatment-experienced genotype 1 and 4 HCV patients with or without compensated cirrhosis will be enrolled in this study.

The inclusion criteria for study are as follows:

1. Male or female 18 years old and above.
2. Be HCV treatment naïve
3. HCV RNA PCR \geq 10,000 IU/L
4. Confirmed infection with Hepatitis C virus (HCV) by HCV serum antibody assay and by HCV Ribonucleic Acid (RNA) Polymerase Chain Reaction (PCR) and Confirmed chronicity with 2 PCR's 6 months apart.
5. Patients with HCV Genotype 1, 4

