- hormonal contraceptive: oral contraceptive pill (estrogen/progestin pill or progestinonly pill), contraceptive skin patch, vaginal contraceptive ring, or subcutaneous contraceptive injection

†Abstinence (relative to heterosexual activity) can be used as the sole method of contraception if it is consistently employed as the subject's preferred and usual lifestyle and if considered acceptable by local regulatory agencies and ERCs/IRBs. Periodic abstinence (e.g., calendar, ovulation, sympto-thermal, post-ovulation methods, etc.) and withdrawal are not acceptable methods of contraception.

0455LH

Enrollment

Upon signing the informed consent, the following data will be gathered prior to start of treatment: demographic data such as age, gender, race/ethnicity, highest educational attainment, employment status, co-morbid conditions as documented in the patient's records, current medications, vital signs (blood pressure, heart rate, respiratory rate, temperature), CBC with differential count, complete metabolic panel, 12-Lead Electrocardiogram (EKG), Cardiac stress test results if applicable, echocardiogram results if applicable, , BMI, baseline HCV RNA PCR

viral load, HCV genotype, baseline HCV resistance testing (if indicated), results of the Fibroscan® test or liver biopsy.

Once the informed consent is signed and the patient is deemed eligible for treatment, the patient will be randomized to either ARM 1 or ARM 2 in a 1:1 ratio. ARM 1 will be prescribed elbasvirir/grazoprevir with/or without ribavirin for 12 or 16 weeks 1 tablet daily with MEMS Smart Cap with real-time monitoring. Arm 2: elbasvir/grazoprevir with/or without ribavirin for 12 or 16 weeks 1 tablet daily MEMS Smart Cap without real-time monitoring.

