	Screening (Day 35 to -1)	Baseline (Day 0)	WK2	Wk4	Wk8	Wk12/16	Wk 4	Wk 12		
	Informed Consent w/ Med Hist inc HIV status	x								
Complete PE inc. Vital Signs	x	x								
Symptom Directed PE inc. Vital Signs			x	X	X	X	x	x		
12-lead ECG	x									
Chemistry(Comprehensive Metabolic Panel)	x	x	x	x	x	x	x	x		
Hematology	x	x	x	x	x	x	x	x		
Virology(HCV)	x	x	x	x	x	x	x	x		
AEs		X	X	X	X	X	X	X		
Con Meds	X	X	X	X	X	X	X			
MEMS download		x	x	x	x	x				

Data Collection

At each visit, the following data are to be collected: HCV RNA PCR viral load, CBC, complete metabolic profile, number of pills missed. For both groups, Number of times pill bottles were opened will also be collected.

Primary outcome measures:

Primary endpoint in the study is the effect of the use of Portal724-MEMS Service on medication adherence, defined as compliance to regimen $\geq 95\%$ of the time.

Secondary outcome measures:

The secondary endpoints for the study include the effect of the use of Portal724-MEMS Service on SVR, factors that affect medication adherence, such as race/ethnicity, age, educational attainment. Additionally, the feasibility of using MEMS adherence technology in an inner city urban population will be evaluated.

Statistical Analysis

This is a pilot study intended to generate initial data on the use of MEMS technology in an inner city population to assess its feasibility and impact on treatment outcomes in HCV infected patients. Wilcoxon signed-rank test will be used to compare Groups 1 and 2 in terms of achieving adherence 95%.

SVR between the groups will also be analyzed in the same manner. A descriptive analysis will be done outlining patients' profiles. Fischer's exact test will be used to compare baseline characteristics between Groups 1 and 2. Alpha level for all statistical analysis will be set at 0.05.

Toxicity management

Grazoprevir/elbasvir

The following side effects have been reported when MK-5172 in doses ranging from 25 mg to 800 mg or placebo (a tablet that looks the same as the MK-5172 but has no active ingredient) was given for up to 12 continuous weeks to 389 HCV-infected men and women at the same time as other drugs commonly given to HCV patients (pegylated interferon and ribavirin). These side effects were considered to be related to the treatment.

- Decrease in the blood cells that carry oxygen
- Decrease in blood cells that fight infection
- Stomach pain
- Diarrhea
- Upset stomach
- Dry mouth
- Nausea
- Vomiting
- Weakness
- Chills
- Fatigue

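### Neither allocation nor analysis uses the 12-week versus 16-week-plus-ribavirin course, which is known at entry and leaves modest but avoidable variance in a 40-patient trial

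*Combined protocol and SAP*

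**What the plan says.** The sample is "40 patients infected with HCV (20 for each group". Under Enrollment, once consent is signed and eligibility is confirmed, "the patient will be randomized to either ARM 1 or ARM 2 in a 1:1 ratio". No strata, blocks, list generation or concealment are described.

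Under Treatment Arms there are six genotype and history groups. Three receive 16 weeks with ribavirin; for example, genotype 1a patients "with baseline NS5A polymorphisms with elbasvir/grazoprevir/ribavirin for 16 weeks". The other three receive 12 weeks. The genotype 1b entry names no drugs, and I read it as without ribavirin. Both randomised arms contain this mix: the control arm is described as "elbasvir/grazoprevir with/or without ribavirin for 12 or 16 weeks 1 tablet daily MEMS Smart Cap without real-time monitoring".

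The determinants are known early. Genotype and, where indicated, resistance results are gathered before treatment, and inclusion criterion 6 requires genotype 1a patients to have resistance testing by screening.

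The background says that adherence to the older interferon regimens was "difficult for many patients due to the length of therapy and the associated side effects of both interferon and ribavirin". It adds that ribavirin is dosed twice a day and that missed doses accumulate as treatment goes on.

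The primary outcome is "medication adherence, defined as compliance to regimen" at least 95% of the time. Both Statistical Analysis sections give an unadjusted comparison of Groups 1 and 2. Baseline characteristics are tested between groups, but no adjustment for them is planned.

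**The concern.** The protocol's own rationale gives a reason to expect lower adherence on the longer, ribavirin-containing course. With 20 patients per arm, chance can easily place several more of these patients in one arm. The estimated effect of real-time feedback would then carry part of the difference between courses. The planned baseline test might show such an imbalance, but the plan offers no remedy for it. The results are meant to inform a larger programme, so precision that costs almost nothing is worth having.

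**Working it through.** The documents state no power, adherence rate by course or course mix, so there is no figure of the plan's own to reproduce. From the documents come N = 40, 20 per arm, 1:1 allocation, the 95% threshold and the two course lengths. The number of long-course patients, K, and the gap g between courses in the share reaching 95% adherence are assumptions, shown as ranges.

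1. **Chance of imbalance.** With a 20/20 split, the number X of long-course patients in one arm is hypergeometric (40, K, 20), and the arms differ by |2X − K|.
   - For K = 4, a difference of 4 means all four fall in one arm: 2 × C(36,20)/C(40,20) = 2 × 7,307,872,110/137,846,528,820 = 10.6%.
   - For K = 8, 12 and 16, the chance of a difference of 4 or more is 23.5%, 30.1% and 33.3%.
   - For K of 3 or fewer it is zero. An odd K allows only odd differences, so its chance can be lower than at neighbouring even values (4.7% at K = 5).

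2. **Shift from a difference of 4.** Shift = (4/20) × g. For g = 10, 20, 35 and 50 points this is 2, 4, 7 and 10 points.

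3. **Typical shift at K = 12.** Var(X) = 20 × 0.3 × 0.7 × 20/39 = 2.154. The difference in long-course share, (2X − 12)/20, has variance 4 × 2.154/400 = 0.02154, so its SD is 14.7 points. One-SD shifts are 1.5, 2.9, 4.4, 5.9 and 7.3 points for g = 10, 20, 30, 40 and 50. The chance of a shift of at least 7 points is 0%, 1.4%, 8%, 30% and 30%.

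4. **What duration alone would do.** The 95% threshold allows 4 missed days in 84 and 5 in 112. If daily adherence is the same on both courses, the share passing is 97.3% v 97.5% at 98% daily adherence, 58.9% v 50.9% at 95%, and 42.8% v 33.1% at 94%. Duration alone therefore gives a gap of about 0 to 10 points. A larger gap would have to come from ribavirin or from adherence falling over time.

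5. **Against sampling error.** The standard error of the arm difference is √(2p(1−p)/20): 15.8 points at p = 50% and 12.6 points at p = 80%.

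6. **Gain from balancing.** Take K = 12, control pass rates of 70% on 12 weeks and 70% − g on 16 weeks, and a 20-point effect in both (assumed). With exact balance, the variance is the sum over arms of [0.7 × p(1−p) + 0.3 × (p−g)(1−p+g)]/20. Without it, add 0.02154 × g².
   - Example, g = 50 points: (0.147 + 0.048 + 0.063 + 0.072)/20 = 0.01650, SE 0.1285. Adding 0.02154 × 0.25 = 0.00538 gives 0.02188, SE 0.1479.

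| Gap g | SE balanced | SE unbalanced | Reduction |
|---|---|---|---|
| 10 points | 0.1285 | 0.1293 | 0.6% |
| 20 points | 0.1319 | 0.1351 | 2.4% |
| 35 points | 0.1328 | 0.1423 | 6.7% |
| 50 points | 0.1285 | 0.1479 | 13.2% |

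Simulation gives similar values: 2% to 3% at 10 to 20 points and 8% to 12% at 35 to 50.

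**The case against.** A reader might infer three stronger things that the documents do not support.

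- **That course is a strong driver and moves the primary result by 7 to 10 points.** With a difference of 4 patients, that needs a gap of 35 to 50 points. No pass rate by course is given. The background text is qualitative and concerns interferon-era regimens; the same section says adherence improved with the newer agents. The endpoint does not say whether ribavirin doses count, and the arm descriptions refer to one tablet a day and a cap on the study drug bottle. If ribavirin doses are not counted, the most direct route to a large gap disappears.
- **That imbalance would bias the comparison.** Chance imbalance averages to zero over randomisations and is already part of the sampling error. In simulations with no effect, 12 of 40 on the long course and gaps of 35 and 50 points, Fisher's exact test rejected about 2% of the time.
- **That 1:1 allocation would miss 20 per group.** This assumes coin-toss allocation, which the protocol never states. A blocked or fixed list would satisfy its wording. What is missing is a description of the method.

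The share on the long course may also be small. Inclusion criterion 2 requires treatment-naïve patients, while Treatment Arms and the study population include experienced ones. If the criterion is applied, only genotype 1a patients with NS5A polymorphisms get 16 weeks.

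Finally, most of the gain comes from the analysis. In simulation at a 35-point gap, the SE was 0.141 unstratified, 0.133 with stratified analysis alone and 0.132 with stratified allocation as well. Power rose only from about 19% to 21%.

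All of this stands and limits the size of the point. It does not remove the omission: the factor is named in the rationale, known at entry and unused.

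**Conclusion.** The point holds as a cheap precision improvement. Course type can be determined before randomisation and is acknowledged as relevant to adherence, yet it enters neither allocation nor analysis. An imbalance of 4 or more patients has a chance of about 11% to 33% at the assumed counts of 4, 8, 12 and 16 long-course patients, and zero at 3 or fewer. It would shift the estimate by 2 to 10 points for assumed gaps of 10 to 50 points. Shifts at the upper end are unlikely unless the gap is about 40 points or more. The cost to the trial is avoidable variance, smaller than the 13- to 16-point sampling error already present. These figures rest on a 20/20 split and on an assumed mix and gap. The mix cannot be narrowed until the treatment-naïve criterion and the treatment-experienced groups are reconciled.

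**What to change.** Randomise from computer-generated lists concealed from enrolling staff, in permuted blocks of varying size within two strata: 12 weeks, and 16 weeks plus ribavirin. This also supplies the missing allocation method and keeps the arms close to 20 each. Compare the 95% endpoint between arms with an exact test stratified by course type. If allocation has already begun, the stratified analysis alone recovers nearly all the gain. State whether ribavirin doses count towards the 95%, and reconcile inclusion criterion 2 with the treatment-experienced groups so that the expected mix can be given.

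The cost is a second list and a stratified test. Incomplete blocks may leave the arms one or two patients apart. No patient's treatment changes.

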We are conducting this study in the hope that we can ensure medication adherence to effectively and cost-effectively treat patients afflicted with chronic Hepatitis C infection. We have chosen HCV since the treatment is finite course (i.e. 12 weeks) which will enable us to measure the efficacy of using Medication Electronic Monitoring System (MEMS) with real-time feedback in terms of increasing adherence within a specific time limit. For this study, we are going to use **Grazopravir/Elbasvir (Zepatier)**, which has an inherent advantage of being a combination pill taken only once a day.

Medication Electronic Monitoring System (MEMS)

Medication Electronic Monitoring System (MEMS) has been used to measure patient compliance to treatment more accurately, especially in clinical trials. It has been determined to be a valid and objective tool to measure medication adherence [24]. Its use to improve compliance has been studied in patients with HIV [20-24], heart failure [26], smoking cessation therapy [27], and in the treatment of alcohol dependence [28]. A few studies have used MEMS in syringes and pill bottle caps to determine proper anti-HCV medication intake [14, 17], but data review and feedback to the patient were only done at each study visit. Real-time health care provider-to-patient feedback may be able to decrease non-adherence but robust studies in this area are still lacking.

There are several different types and manufacturers of commercially available MEMS. For this study, we are proposing to use the Portal724-MEMS Service. The Portal724-MEMS is a TURNKEY SERVICE. It integrates medication bottle, Smart Cap, Pill Dispenser, Embedded Computer, Embedded Cellular Modem and Tamper Proof apparatus. This device is capable of transmitting pill dispensing events from the patient's home to the Cloud over Cellular and IP networks. The transmission is done in real time if cellular coverage is above 1-bar, but if cell is not available or if the signal is below threshold, then the device Store-and-Forward feature is automatically activated.

The bottle cap records the number of Pill Dispenses, with date and time and Device ID. The purpose of this electronic monitoring is to estimate compliance with medication regimen.

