For Group 1, the cap of the study drug bottle will be replaced with the Portal724- MEMS Smart Cap. A cellular phone per patient will also be provided. The Smart Cap in this study is to be outfitted to send messages to a website to which only the investigators and the research assistants have access to monitor medication adherence. Patients are to be instructed to open their study drug bottles in areas where there is at least 1 cellular signal bar. Patients will also be instructed to take their medications at specific agreed upon times. Once the agreed upon times are set, these will be programmed into the Smart Caps through a software program. The Smart Caps are encoded to not only record each pill bottle opening, it also will transmit an alert to the aforementioned website when the bottle is not opened within 2 hours of the agreed upon time. This alert is then seen by the Investigator or the Research assistant through a computer or their smartphone. The Investigator or Research Assistant in turn calls the cellular phone provided to the patient to remind the participant to take their medication, thus providing real-time feedback. Group 2 (the control group) will be provided MEMS Smart Cap to record study drug bottle opening, but without real-time feedback and will be managed as per the standard of care at the Liver Center SMMC.

Patients from both groups will be seen in the Liver Center at Day 1, weeks 2, 4, 8 and 12 from start of treatment. They will be seen by Liver Center Physician together with the Investigator and Research Assistant at each visit. They will also be counseled about the importance of medication adherence at every visit by the Liver Center physician. At each visit, patients are instructed to bring with them all of their anti-HCV study drug bottles for pill counting to be done by the Investigator and Research Assistant. Patients in ARM 1 will also get feedback about their medication compliance using the Smart Caps per visit.

After completion of treatment as determined by the Liver Center Physician, patients from both groups are to follow-up at week 4 and week 12 post-treatment. At that time, an HCV RNA PCR viral load will be obtained to determine if patient has an undetectable viral load, or Sustained Virologic Response (SVR). SVR is the marker for a functional cure of HCV, or treatment success. Non-SVR would mean treatment failure.

Study Procedures	Pre-Treatment						Treatment Assessments		Post Tx	Post tx

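### The Group 1 signal instruction covers only opening the bottle, but the reminder call depends on an alert sent from a bottle that has stayed closed

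*Combined protocol and SAP*

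**What the plan says.** The signal is discussed in two places.

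- **Device description** (section Medication Electronic Monitoring System (MEMS)): "The transmission is done in real time if cellular coverage is above 1-bar". With no cellular service, or "if the signal is below threshold, then the device Store-and-Forward feature is automatically activated".
- **Patient instruction** (Enrollment, paragraph on Group 1): "Patients are to be instructed to open their study drug bottles in areas where there is at least 1 cellular signal bar".

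The same Enrollment paragraph describes how the intervention works. The agreed dosing times are programmed into the Smart Cap. The cap records each opening, and "it also will transmit an alert to the aforementioned website when the bottle is not opened within 2 hours of the agreed upon time". The investigator or research assistant sees the alert and then "calls the cellular phone provided to the patient to remind the participant to take their medication, thus providing real-time feedback". Group 2 has the same cap for recording but receives no real-time feedback.

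No section says where the bottle should be kept between doses, what signal is needed there, or what staff should do with an alert that arrives late.

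**The concern.** The instruction secures the signal at one moment, when the bottle is opened. The reminder is triggered by the opposite event, a bottle left closed past its time. On a day when a dose is forgotten, the cap has to transmit from wherever the bottle happens to be. Someone who carries the bottle to a window each morning and otherwise keeps it in a basement cupboard complies fully. That person may still get no timely call on the days when a call is needed.

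What is at stake is delivery of the Arm 1 intervention. Both arms have the cap and counselling at visits. Arm 1 differs by the real-time alert and call, together with feedback from the cap data at visits. If alerts arrive late for some Arm 1 patients, those patients move towards the control condition. Unless late alerts are counted, a null result could not separate feedback that does not help from feedback that did not arrive. The second question belongs to the feasibility aim in the secondary outcome measures.

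**Working it through.** **1. The two signal rules side by side**

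| Signal | Patient instruction (at least 1 bar) | Real-time transmission (above 1 bar) |
|---|---|---|
| None | not met | not met |
| Exactly 1 bar | met | not met on a literal reading |
| 2 bars or more | met | met |

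The rules differ in one row only. That row is itself unclear, because store-and-forward starts when the signal is below a threshold that is never given a number. If the threshold is 1 bar, a 1-bar signal is not below it.

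**2. Which event needs signal, and where**

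| Event | Where the cap must have signal | Covered by the instruction? |
|---|---|---|
| Opening is recorded and sent | where the bottle is opened | yes |
| Missed-dose alert is sent | where the closed bottle is kept | no |

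The second row is the gap, and it exists whichever threshold applies.

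**3. How few doses decide the endpoint**

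The Objective sets adherence as "defined as compliance to regimen 95% of the time". Assume that this means doses taken divided by once-daily doses scheduled, which the documents do not spell out.

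- 12 weeks: 7 × 12 = 84 doses; 0.95 × 84 = 79.8, so 80 are needed and at most 4 may be missed (80/84 = 95.2%; 79/84 = 94.0%).
- 16 weeks: 7 × 16 = 112 doses; 0.95 × 112 = 106.4, so 107 are needed and at most 5 may be missed (107/112 = 95.5%; 106/112 = 94.6%).

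A few untimely alerts could therefore change how a patient is classified.

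**4. Illustrative worst case for the comparison**

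The plan has no power figure to reproduce. The only inputs from the documents are 20 patients per group and alpha 0.05 (Methods; Statistical Analysis). The adherence rates and the fraction f of Arm 1 without signal are assumptions. A patient without signal is given exactly the control rate:

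Arm 1 rate = p1 × (1 − f) + p0 × f

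Power is for the exact two-sided Fisher test. It was found by summing the probability of every pair of binomial outcomes (0 to 20 in each arm) with p ≤ 0.05.

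| Control p0 | Arm 1 p1 | f | Arm 1 rate | Power |
|---|---|---|---|---|
| 60% | 90% | 0 | 90% | 0.49 |
| 60% | 90% | 10% | 0.9 × 0.9 + 0.6 × 0.1 = 87% | 0.38 |
| 60% | 90% | 20% | 0.9 × 0.8 + 0.6 × 0.2 = 84% | 0.29 |
| 60% | 90% | 30% | 0.9 × 0.7 + 0.6 × 0.3 = 81% | 0.21 |
| 50% | 80% | 0 | 80% | 0.41 |
| 50% | 80% | 30% | 0.8 × 0.7 + 0.5 × 0.3 = 71% | 0.18 |
| 70% | 95% | 0 | 95% | 0.45 |
| 70% | 95% | 30% | 0.95 × 0.7 + 0.7 × 0.3 = 87.5% | 0.17 |

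Fisher's test is used here because the outcome is adherent or not in two independent groups. The Statistical Analysis section names a different test for this comparison.

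**The case against.** The strongest reply is that this is a small operational gap in a pilot. Feasibility is a stated secondary endpoint and the primary objective is the effect of using the service, so signal failures in real homes are arguably part of what is being studied. Signal at opening does matter, because openings are what the device sends to the website. The instruction is therefore incomplete rather than misdirected. All of this stands. It does not remove the gap, because the feasibility question can be answered only if late alerts are counted, and nothing in the plan counts them.

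The power figures are also open to challenge, and the challenge stands. They treat every patient without signal as a control for the whole course. That means that no alert arrives in time, a late call does nothing, and the cap feedback given to Arm 1 at visits adds nothing. They bound the loss under the assumed rates and do not estimate it.

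Three stronger readings may tempt a reader, and the documents do not support them:

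- **That the device fails at 1 bar, so the instruction is wrong.** The threshold for store-and-forward is not given a number, so exactly 1 bar can be read either way.
- **That adherence data would be lost.** Openings are stored and forwarded, and the Study Procedures table lists a MEMS download at baseline and at weeks 2, 4, 8 and 12/16. The Data Collection section adds missed-pill counts.
- **That a delayed opening record could prompt a call about a dose already taken.** This needs the website to work out missed doses for itself. The Enrollment section instead has the dosing times programmed into the cap and the cap sending the alert.

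**Conclusion.** The point holds in a limited form. The main part is the missing requirement on signal where the closed bottle is kept. The mismatch in wording is secondary and matters only at exactly 1 bar.

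The consequence is weaker delivery of real-time feedback in Arm 1, by an amount that the documents do not allow anyone to estimate. In the worst case above, with 30% of Arm 1 lacking signal, power falls by more than half for all three assumed pairs of rates (0.49 to 0.21, 0.41 to 0.18, 0.45 to 0.17). With 10% lacking signal, at 60% against 90%, it falls to 0.38.

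One further assumption applies. The documents describe store-and-forward for dispensing events and do not say whether a missed-dose alert is held and sent in the same way. Whether the alert arrives late or not at all, a timely call would not follow.

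**What to change.** 1. State one signal threshold, confirmed against the device specification, and use the same wording in the MEMS section and the Enrollment section.
2. Extend the Group 1 instruction: patients should keep the bottle, as well as open it, where the signal meets that threshold.
3. If the website logs receipt times, report how many Arm 1 alerts arrived late, as part of the feasibility endpoint. An alert is due 2 hours after the programmed dosing time if the downloaded record shows no opening by then, so lateness is receipt time minus due time. The MEMS section says that the cap records dispenses with date, time and device ID. It mentions no transmission or receipt time and no marker for stored events, so the availability of a receipt log should be checked first.

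The first two changes cost a sentence each. The third costs one descriptive summary if the log exists, and otherwise a request to the device supplier. None of them alters the sample size, the visits or the randomisation.

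### If bottle openings define adherence of at least 95%, the Group 1-only alerts, calls and cap feedback act on the measuring device in one arm and can produce an apparent benefit at equal intake

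*Combined protocol and SAP*

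**What the plan says.** The Enrollment section of the combined protocol and SAP describes Group 1's cap as programmed with agreed dosing times, and "it also will transmit an alert to the aforementioned website when the bottle is not opened within 2 hours of the agreed upon time". The investigator or research assistant then telephones the patient with a reminder. Arm 1 patients also receive feedback from the cap data at each visit. Group 2 has a cap that records openings, without real-time feedback.

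Two adherence records exist in both arms. Under Data Collection, for both groups, "Number of times pill bottles were opened will also be collected", and the number of pills missed is listed at each visit. Under Enrollment, "patients are instructed to bring with them all of their anti-HCV study drug bottles for pill counting".

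The primary outcome is "medication adherence, defined as compliance to regimen" at least 95% of the time. No section says which record decides whether a patient meets it, or what happens when the two disagree. The device description under Medication Electronic Monitoring System says that the cap counts pill dispenses, whereas Enrollment and Data Collection speak of openings. The plan does not mention doses taken from outside the bottle or openings without a dose.

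**The concern.** The intervention is triggered by the absence of an opening, and the opening may also be the outcome. A Group 1 patient who carries pills on a trip or fills an organiser will trigger an alert, receive a call and see the gap at the next visit. Each of these pushes the patient towards using the bottle for every dose, or simply towards opening it. Group 2 has no such pressure.

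Two errors can follow, and both favour Group 1: off-bottle doses that persist as misses in Group 2, and empty openings that count as doses in Group 1. Randomisation does not protect against them, because they arise after allocation and are caused by the intervention. The trial is also open-label. The pilot is meant to inform a larger programme, so it should be able to tell better intake from better bottle handling.

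**Working it through.** **Inputs from the plan.** One tablet daily for 12 or 16 weeks gives 12 × 7 = 84 or 16 × 7 = 112 doses. The threshold is at least 95%. There are 20 patients per group, "randomized to either ARM 1 or ARM 2 in a 1:1 ratio". On the significance level: "Alpha level for all statistical analysis will be set at 0.05"; sidedness is not stated, and two-sided is assumed here.

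**Assumptions, none of them in the plan.** The true miss rate is 3% in both arms. Doses on a further 1% or 2% of days are taken but not from the bottle. In Group 1 the prompts convert all, half or none of these into openings; in Group 2 none are converted.

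**No figure of the plan's own to reproduce.** It states no expected adherence rate, effect size or power.

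**Step 1, tolerance.** 0.95 × 84 = 79.8, so 80 openings are needed and 4 may be missing. 0.95 × 112 = 106.4, so 107 are needed and 5 may be missing. One or two unrecorded doses can therefore reclassify a patient.

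**Step 2, chance of being classed adherent on 84 doses.** This is P(X ≤ 4), with X binomial(84, apparent miss rate), or beta-binomial with intraclass correlation 0.05 to allow for differences between patients.

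| Apparent miss rate | Identical patients | Correlation 0.05 |
|---|---|---|
| 3% | 0.892 | 0.806 |
| 3.5% | 0.828 | 0.767 |
| 4% | 0.754 | 0.728 |
| 5% | 0.589 | 0.650 |

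**Step 3, spurious difference (Group 1 minus Group 2) at equal intake.**

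| Off-bottle days | Converted in Group 1 | Apparent miss rates | Identical patients | Correlation 0.05 |
|---|---|---|---|---|
| 1% | all | 3% v 4% | 0.892 − 0.754 = 14 points | 0.806 − 0.728 = 8 points |
| 2% | all | 3% v 5% | 0.892 − 0.589 = 30 points | 0.806 − 0.650 = 16 points |
| 1% | half | 3.5% v 4% | 0.828 − 0.754 = 7 points | 0.767 − 0.728 = 4 points |
| 2% | half | 4% v 5% | 0.754 − 0.589 = 17 points | 0.728 − 0.650 = 8 points |
| 1% or 2% | none | equal | 0 | 0 |

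For 112 doses with full conversion, the differences are 17 and 37 points with identical patients, and 8 and 17 with correlation 0.05.

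**Step 4, effect on a significance test.** The plan says "Wilcoxon signed-rank test will be used to compare Groups 1 and 2 in terms of achieving adherence" 95% or above. That test is for paired data and these groups are independent, so an exact two-sided Fisher test at 20 v 20 is used here. With 84 doses and full conversion, it rejects in about 12% (1% off-bottle) or 49% (2% off-bottle) of trials if patients are identical, and in about 5% or 12% with correlation 0.05. With equal apparent rates it rejects in about 2%. Nearly all of the excess favours Group 1.

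**The case against.** Four objections have force.

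First, a reader might infer that the alerts detect doses taken outside the bottle. They do not. An alert shows only that the bottle was not opened, and the call is described as a reminder, with no question about doses already taken. Any bias needs the prompts to change how patients use the bottle. That is plausible, since changing behaviour around the opening is the purpose of the alert, but it is an inference.

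Second, a reader might take openings to be the primary measure. The plan does not say so. On pill counts, tablets removed in advance count as used and empty openings add nothing, so both mechanisms disappear. Openings remain a likely source: the Introduction calls pill counting imprecise, the MEMS section gives estimating compliance as the purpose of the monitoring, and cap downloads are scheduled.

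Third, if the cap counts dispenses, pills removed early are still counted, only at the wrong time, and an opening that dispenses nothing is not a dose. The document supports both descriptions of the device.

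Fourth, the plan's silence does not show that Group 2 receives no dosing instructions. The agreed times and the instruction on where to open the bottle appear in the description of Group 1, but adherence counselling and bottle return apply to both arms. Patients unwilling to follow instructions on taking the medication are excluded from either arm.

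These make the concern conditional but do not remove it. If openings decide the endpoint, the unequal pressure on bottle use remains.

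**Conclusion.** The point holds conditionally. If openings define the endpoint, the prompts given only to Group 1 can create a difference in its favour when intake is equal. Naming openings as the source would not cure this.

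The documents do not support reading 14 to 30 points as the expected bias. Those figures assume identical patients and off-bottle dosing removed completely in Group 1 from the first dose. With between-patient variation the range is 8 to 16 points. Half conversion roughly halves either range, and no conversion gives zero. The miss rate, off-bottle rates, conversion share and correlation are all assumed. What comes from the plan is the narrow tolerance of 4 doses in 84, or 5 in 112, which makes classification sensitive to a few unrecorded doses.

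For a pilot this is a worthwhile correction. It bears mainly on whether a positive result may be described as improved intake.

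**What to change.** 1. On Day 1, give both arms the same written bottle-use instruction: each dose straight from the capped bottle, one opening per dose, no advance removal and no organiser.
2. State whether the cap counts dispenses or openings, make the device description agree with Enrollment and Data Collection, and name the record that defines the 95% endpoint.
3. Repeat the primary comparison of adherence of at least 95% using the pill counts already taken in both arms.
4. Report openings minus pills used, by arm, with a confidence interval for the difference between arms. A shortfall of openings in Group 2 would point to off-bottle dosing, and an excess in Group 1 to empty openings. The two can cancel within an arm, so show the distribution across patients as well as the mean.
5. State in advance that a benefit seen on openings but not on pill counts will be reported as improved bottle use and not as improved intake.

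Opening records should not be corrected from patient recall. In an open-label trial where only one arm was called about unopened days, recall can itself differ by arm.

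The cost is one instruction sheet and two analyses of data already collected; the alerts and calls stay as they are. There are two downsides. Pill counts are imprecise and do not prove ingestion, and the instruction slightly changes how the control arm handles its bottles compared with usual care.
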